5.2.2. Safety Measures

Descriptive summaries of safety measures will be based on observed data only. No imputation of missing scores will be implemented.

5.2.3. Dates for Medical Events and Medications

Completely or partially missing onset and resolution dates for AEs, Concomitant Medications (CM), and Medical History (MH) will be imputed in a conservative fashion as follows:

Incomplete Adverse Event Onset Date

- 1. Year imputation
 - If *year* is missing (or AE onset date is completely missing), then the onset date will not be imputed.
- 2. *Month imputation*
 - If *year* is not missing but *month* is missing, then:
 - If *year* = year of first study dose date, then set the *month* and *day* to the day and month of first study dose
 - Else if *year* \neq year of first study dose: set *month* to January
- 3. *Day imputation*
 - If *day* is missing (*month and year* not missing), then:
 - If year = year and month = month of first study dose, then set day to day of first study dose
 - Else if *year* ≠ year or *month* ≠ month of first study dose, then set *day* to first day of the *month* in the *year*

Incomplete Adverse Event Resolution Date

- Do not impute if any resolution date is missing
- If the duration of AE is needed, the following approach may be considered:
 - If year is missing (or AE resolution date is completely missing): do not impute
 - If *year* is not missing but *month* and *day* are missing: impute December 31st for missing *month* and *day*
 - If *year* and *day* are not missing but *month* is missing: impute December for missing *month*
 - If *year* and *month* are not missing but *day* is missing: impute last day of the *month* for missing *day*.

Incomplete CM or MH Onset Date

- 1. If year is missing (or CM/MH onset date is completely missing): do not impute
- 2. If *year* is not missing but *month* and *day* are missing: impute January 1st for missing *month* and *day*
- 3. If year and day are not missing but month is missing: impute January for missing month
- 4. If year and month are not missing but day is missing: impute 01 for missing day

Incomplete CM or MH Resolution Date

- Do not impute if any resolution date is missing.
- If the duration of event is needed, the following approach may be considered:

- If year (or resolution date is completely missing): do not impute
- If *year* is not missing but *month* and *day* are missing: impute the last day of the *year*
- If *year* and *day* are not missing but *month* is missing: impute the last month of the *year* for the missing *month*
- If *year* and *month* are not missing but *day* is missing: impute the last day of the *month* of the *year*

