3.4. Visits and Assessments

The schedule of activities (SoA) is provided in Table 1.

	Screening		Double-Masked Period Visits					Open-Label Period Visits							
	Screening (Within 30 days prior to D1; i.e., D -30 to D -1)	E (Base	01 eline)	D14	M1	NN	12, 14	M3	M5	N	16 ^a	M7, M9, M11	N M	18, [10	M12/ Exit/ Early Termina- tion
Study day		E	01	D14	D30	D D	60, 120	D90	D150	D	0180	D210, D270, D330	D2 D2	240, 300	M12: D360
Visit window in days	NA	N	IA	±2	±3	H	⊨ 3	±3	±3	:	±7	±7	=	±7	M12: ±7
IP (DE-109, Sham, Dummy) administration		x	b			Х	, b				X			X	
Time relative to IP administration		pre	post			pre	post			pre ^a	post ^a		pre	post	
Signed and dated informed consent	x ^c														
Inclusion/exclusion criteria	X	x													
Medical/surgical history, history of NIU-PS	x														
Demographics	X														
Physical examination and vital signs	x								x ^d						X
VFQ-25		x							x ^d						X
Serum pregnancy test ^e	x ^e														x ^e
Urine pregnancy test ^e		x ^e				x ^e				x e			x ^e		
Laboratory safety tests (hematology, chemistry, urinalysis) ^f	x ^f								x ^{d, f}						x ^f
Blood sample for pharmacogenomics ^g				x ^g											
Time relative to IP administration		pre	post			pre	post			pre ^a	post ^a		pre	post	
Randomization ^h		x ^h													

	Screening		Double-Masked Period Visits						Open-Label Period Visits						
	Screening (Within 30 days prior to D1; i.e., D -30 to D -1)	E (Bas	01 eline)	D14	M1	N N	12, 14	M3	М5	N	16 ^a	M7, M9, M11	N N	18, 110	M12/ Exit/ Early Termina- tion
Best-corrected visual acuity (ETDRS)	X	x		x	x	x		x	x	x		x	x		x
Slit-lamp biomicroscopy	X	x	x ⁱ	x	x	x	x ⁱ	x	x	x	x ⁱ	x	x	x ⁱ	x
Intraocular pressure	X	x	x ^j	x	x	x	x ^j	x	x	x	x ^j	x	x	x ^j	X
Indirect ophthalmoscopy	X	x	x ⁱ	x	X	x	x ⁱ	x	x	x	x ⁱ	x	x	x ⁱ	X
Optical Coherence Tomography		x		x	x	x		x	x	x		x	x		x
Fundus photography	X	x		x	x	x		x	x	x		x	x		X
Fluorescein angiography k		x						x	x						x
Systemic corticosteroid medication status	x ¹	x		x	x	x		x	x	x		x	x		X
Other prior or concomitant medications	X	x	x	x	x	x	x	x	x	x	x	x	x	x	x
Prednisolone acetate eye drops ^m			x ^m				x ^m				x ^m			x ^m	
Adverse events ⁿ	X	x	X	x	х	x	x	x	x	х	x	x	x	x	x

Table 1:Table of Activities (Continued)

IP = Investigational product; NA = not applicable; M=Month; D=Day; pre=prior to IP administration; post = after IP administration.

^a The double-masked period ends with the pre-dose evaluations at Month 6; the first open-label dose of DE-109 is at Month 6.

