4.4. Treatment Period, Treatment Start Date, and Treatment End Date

Treatment start date and treatment end date for each treatment period are defined as follows in

Treatment Period	Treatment Start Date	Treatment End Date
Double-Masked (DM) Treatment Period	The date at which a randomized subject received the first injection of DE-109 or the first Sham procedure	The date of the last double-masked injection of DE-109 + 120 days, the date of the first injection of the open-label DE-109 440 μ g, or the Study Exit date, whichever came first
Open-Label (OL) Treatment Period	The date of the first open-label injection of DE-109 440 µg	The date of the last open-label injection of DE-109 440 μ g + 120 days, or the Study Exit date, whichever came earlier
Entire Study	The date at which a randomized subject received the first injection of DE-109 or the first Sham procedure	The date of the last open-label injection of DE-109 440 μ g + 120 days, or the Study Exit date, whichever came earlier

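### Partial adverse-event onset dates have no open-label anchor, so in every arm some open-label events are dated back into the double-masked period, and in sham subjects DE-109 events become sham events

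*SAP*

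**What the plan says.** SAP 5.2.3 says that incomplete event dates "will be imputed in a conservative fashion as follows". For adverse-event onset the steps are:

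- Year missing: "then the onset date will not be imputed".
- Month missing, year equal to that of the first study dose: "then set the *month* and *day* to the day and month of first study dose".
- Month missing, any other year: "set *month* to January".
- Only the day missing: the first-dose day if month and year match the first dose, otherwise the first of the month.

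No step uses the first open-label injection, the visit at which the event was reported, or the end date.

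Other sections make the onset date decide where an event is counted. SAP 3.1 gives every subject DE-109 440 µg in the open-label period, and SAP Table 1 notes that "the first open-label dose of DE-109 is at Month 6". SAP 4.4 lists "the date of the first injection of the open-label DE-109 440" µg among the dates that can end the double-masked period, and it starts the open-label period on that same date. SAP 9.1.1 plans separate adverse-event tables for the two periods, and SAP 9.2 tabulates by actual treatment received.

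**The concern.** The rule is conservative for one question: whether an event is treatment-emergent after the first administration. It does not suit the other question that these tables answer, namely which treatment the subject was on at onset. For a subject randomised to sham, the first study dose is a sham procedure and DE-109 starts only at Month 6. Moving an open-label onset to Day 1, to 1 January or to the first of the month can place it before any DE-109 exposure.

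At stake are the sham column of the double-masked safety table, which would contain events that arose on DE-109, and the open-label table, which would lose them. The day-only case falls in the calendar month of the first open-label injection. For sham subjects that is the first real intravitreal injection, and Protocol 9.5.4 plans a separate tabulation of injection-related events.

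**Working it through.** There is no figure in the plan to reproduce: neither document gives the number of partial dates or the expected share misplaced.

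**Inputs.** The onset rule is from SAP 5.2.3. The first open-label dose is at Day 180 ± 7 and the last visit at Day 360 (SAP Table 1). Two assumptions are not in the documents: first doses are spread evenly over a calendar year, and open-label onsets are spread evenly from the first open-label injection to Day 360.

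**Example dates (hypothetical).**

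| First dose | First open-label injection | True onset | Recorded as | Imputed onset | Period |
|---|---|---|---|---|---|
| 10 Mar 2021 | 5 Sep 2021 | 20 Oct 2021 | 2021 | 10 Mar 2021 | double-masked |
| 12 Oct 2020 | 9 Apr 2021 | 20 May 2021 | 2021 | 1 Jan 2021 | double-masked |
| 10 Mar 2021 | 5 Sep 2021 | 20 Sep 2021 | Sep 2021 | 1 Sep 2021 | double-masked |
| 10 Mar 2021 | 5 Sep 2021 | 20 Oct 2021 | Oct 2021 | 1 Oct 2021 | open-label |
| 10 Mar 2021 | 5 Sep 2021 | 20 Jan 2022 | 2022 | 1 Jan 2022 | open-label |

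**Month and day missing, closed form.** Let u be the first-dose time, uniform on one year. The open-label period runs from u + 0.5 to u + 1.0 years.

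- If u < 0.5, onsets up to the year end (length 0.5 − u) go to the first-dose date and are misplaced. Later ones go to 1 January, after the open-label start, and stay.
- If u ≥ 0.5, the whole open-label period lies in the next year. All its onsets go to 1 January of that year, before the open-label start, and are misplaced (length 0.5).

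Misplaced time = ∫₀^0.5 (0.5 − u) du + ∫_0.5^1 0.5 du = 0.125 + 0.25 = 0.375. As a share of 0.5 years this is 0.375 / 0.5 = 75%.

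**Only the day missing.** About 15 days remain on average in the calendar month of the first open-label injection, out of about 180 open-label days: 15 / 180 = 8%.

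**Day-by-day check.** The rule was applied to all 365 first-dose days and every onset day, with the first open-label dose at Day 173, 180 and 187.

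| Missing part | Open-label onsets moved into double-masked | Double-masked onsets moved into open-label |
|---|---|---|
| Month and day | 74–76% | 0% |
| Month only | 70–72% | 0% |
| Day only | 7.8–8.5% | 0% |

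The error between periods runs one way only. These are shares of partially dated open-label events, not of all adverse events. The calculation does not depend on the arm.

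**The 120-day window.** SAP 9.1.1 extends treatment emergence to 120 days after the treatment end date. If the double-masked period ends at the first open-label injection on Day 180, fully dated onsets on Days 180 to 300 also meet the double-masked definition: 121 of the 181 days from Day 180 to Day 360, or 67%.

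**The case against.** A reader might infer that the rule biases the masked comparison in favour of DE-109 by raising sham rates. The documents do not support that. The same rule applies to all arms, and subjects randomised to DE-109 440 µg also receive open-label injections, so their partially dated open-label events are pulled back into the DE-109 masked column in the same way. The net effect on the difference depends on partial-date event counts by arm, which are not given. Nor does the rule always choose the earliest possible day: a missing year is not imputed, and events in the first-dose month go to the dose day.

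The practical weight is limited. Adverse events are assessed at every visit, injection visits include examinations within about an hour, and serious events and events of special interest are reported within 24 hours, so the important events are the least likely to lack a date. Safety is descriptive, without testing, and events are also listed.

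Loss from the open-label table is also not quite certain. SAP 9.1.1 excludes an event only where an onset before treatment start can be determined, and the SAP does not say whether an imputed date counts as such a determination.

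Finally, the 120-day window already blurs the periods, so a better date rule alone would not separate them.

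All of this stands, and it limits the point without removing it. The stated rule, followed as written, still gives a sham subject's DE-109 event an onset before any DE-109 was given.

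**Conclusion.** The point holds as a minor one. SAP 5.2.3 lacks an anchor for the treatment switch at Month 6. It therefore dates some open-label events into the double-masked period in every arm, and never the reverse. In sham subjects this is misattribution of drug events to control. In all arms the open-label table loses the event if the imputed date is taken as the onset date.

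Under even accrual, the share is about 75% with month and day missing and about 8% with only the day missing. Both depend on the uniform-spread assumptions, and the absolute effect depends on an unstated, possibly small, number of partial dates. No direction of bias in the DE-109 versus sham difference is established.

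**What to change.** Amend SAP 5.2.3 before unmasking, identically for all arms:

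1. Bound the imputed onset first by the known date parts, the visit of first report together with the previous visit without the event, and the end date.
2. If the event was first reported after the first open-label injection and the known parts are compatible with onset on or after it, set onset to that injection date and count the event as open-label. The explicit count is needed because SAP 4.4 makes that date both the end of one period and the start of the next.
3. Otherwise keep the present rule.

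The change should not be restricted to sham subjects, because the same partial date would then be treated differently by arm.

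SAP 4.4 and 9.1.1 should be reconciled at the same time, so that the 120-day extension does not carry fully dated open-label events into the double-masked table.

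The cost is a short SAP amendment and a small programming change. Protocol Appendix 3 does not list the visit of first report among the adverse-event form items, so it may have to be derived from visit or entry dates. The downside is that a few true double-masked events with no other evidence may move to open-label. Conditioning on the report visit keeps this small: an unconditional open-label anchor, under the same assumptions, would move about 74–76% of true double-masked events with the month missing and about 8–9% of those with only the day missing.

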5.3. Multi-Center Studies

This is a multicenter study with approximately 72 centers, among which a maximum of 35 centers are planned to be outside of the United States. The number of subjects per site might be small. Therefore, there are no analyses adjusting for sites.

5.4. Multiple Comparisons / Multiplicity

To control the overall Type I error rate associated with the multiple comparisons on the primary and the key secondary endpoints at the 0.05 level (two-sided), the following hierarchical testing strategy will be employed:

- A. Conduct the statistical testing for the primary comparison between DE-109 440 μg and Sham treatment arm on the primary endpoint (VH 0 response) at the significance level of 0.05 (two-sided)
- B. If the result of the primary comparison on the primary endpoint is positive (i.e., *p*-value < 0.05), then conduct the statistical testing for the primary comparison between DE-109 440 μg and Sham treatment arm on the following key secondary endpoints in a hierarchical fashion:
 - 1. Mean composite score at Month 5
 - 2. VH 0 response at Month 3
 - 3. Mean composite score at Month 3

The primary comparison on the $(i+1)^{th}$ key secondary endpoint will be performed inferentially ONLY IF the result of the primary comparison in the ith key secondary endpoint is positive, where i = 1 or 2.

5.5. Interim Analysis and Data monitoring Committee

An independent data monitoring committee (DMC) whose members will not be participating in the LUMINA study conduct will serve as an advisory board to the Santen senior management team. The DMC will periodically review and make recommendations based on interim data; unmasked data will only be reviewed in closed DMC sessions without participation of Santen personnel. The organization, responsibilities, and procedures of the DMC will be specified in a governing charter.

An interim analysis is planned when the first 100 subjects complete their Month 5 Visit. The DMC is authorized to evaluate unblinded interim efficacy and safety analyses. Study sites will

receive information about interim results only if they need to know for the safety of their patients.

5.5.1. Interim Analysis

The objectives of the interim analysis are to assess for futility and to re-assess the sample size. No analyses are planned for the purpose of stopping the study early for efficacy. The futility and sample size re-assessment are based on evaluation of conditional power in relationship to pre-specified decision rules defined by ranges of attainable conditional power values under the "promising zone" approach (Mehta et al., 2011). If the conditional power is less than 30%, futility will be recommended and the study may stop for futility. If the conditional power is between 50% and 80%, the sample size will be increased up to 100 extra subjects. If the conditional power between 30% and 50% or greater than 80%, no change to the sample size will take place.

The futility and sample size re-assessment analysis will be evaluated for the primary endpoint, vitreous haze (VH) 0 response at Month 5 based on subjects who were randomized, received at least one dose of IP at baseline, and reached or completed Month 3 visit of the study. Missing VH status at the interim analysis will be handled using the multiple imputation approach in the similar manner as specified in Section 8.2.1. However, only number of enrolled eye will be used as the stratification factor in the Cochran-Mantel-Haenszel (CMH) test procedure (Yu et al., 2020).

The conditional power at the interim analysis, denoted by $CP_{\delta_1}(z_1, \widetilde{n_2})$, can be defined by the following equation (Mehta et al., 2011):

$$CP_{\widehat{\delta_1}}(z_1, \widetilde{n_2}) = 1 - \Phi\left(\frac{z_{\alpha/2}\sqrt{n_2} - z_1\sqrt{n_1}}{\sqrt{\widetilde{n_2}}} - \frac{z_1\sqrt{\widetilde{n_2}}}{\sqrt{n_1}}\right)$$

where n_1 is the number of evaluable subjects at the interim analysis, n_2 is the total number of subjects at the final analysis, $\tilde{n_2} = n_2 - n_1$, $z_{\alpha/2} = \Phi^{-1}(1 - \alpha/2)$, and z_1 is the squared root of the CMH test statistic as computed at the interim analysis of n_1 evaluable subjects. Define the estimated treatment difference, $\hat{\delta_1} = \hat{\pi}_{440} - \hat{\pi}_{\text{sham}}$ at interim analysis, where $\hat{\pi}_{440}$ and $\hat{\pi}_{\text{sham}}$ are Mantel-Haenszel weighted response rates of DE-109 440 µg and Sham arms at interim analysis, respectively.

The primary analysis of this study is the analysis of the data from the 6-month, double-masked period. These data will be quality-checked, soft-locked, and the analysis for double-masked period will be conducted after all subjects have completed the Month 6 visit or prematurely discontinued from the study prior to Month 6.

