Study eyes which were rescued due to worsening of uveitis specified under previous protocol version but did not meet the rescue criteria under the current version will be treated as rescued due to other reason and censored the data after being rescued. The multiple imputation-based approach will be applied to impute missing VH score data of study eyes which were not rescued and treated as non-responders. The VH 0 response status will then be determined based on the observed or imputed VH score.

For missing VH score due to any other reasons other than protocol-specified worsening of uveitis, the multiple imputation approach will be applied as follows:

- 1. Use Markov chain Monte Carlo (MCMC) to create monotone missingness first with VH score on the logarithm scale. Then obtain standard multiple imputations under MAR assumptions for missing VH scores using monotone regression on the logarithm scale. The imputed values will be then converted into an eligible VH score based on the absolute distance. The missing data are filled in and 50 complete datasets are created. The seed that will be used in the SAS program is 135711.
- 2. Each of 50 complete datasets will then be analyzed separately. The CMH test statistic, response rate for each treatment group, and the rate difference will be calculated for each complete sets.
- 3. The final CMH test statistic, obtained from each complete dataset, will be transformed using Wilson-Hilferty transformation and combined for inference purposes (O'Kelly et al., 2014). Rates and rate differences will also be combined without any transformations.

The Mantel-Haenszel weighted response rate (%) of each treatment group, the Mantel-Haenszel weighted rate difference, the corresponding asymptotic 95% confidence interval (CI) and the CMH's p-value will be reported.

The main part of the SAS code for the specified CMH test procedure and the multiple imputation are provided in Appendix C, respectively.

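### The interim analyses Month 5 response in everyone who has reached Month 3 but has no allowance for imputed outcomes, so conditional power is biased low; z1 also loses its sign

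*SAP*

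**What the plan says.** SAP 5.5 and Protocol 9.6 set the same trigger: "An interim analysis is planned when the first 100 subjects complete their Month 5 Visit". SAP 5.5.1 fixes the endpoint: "The futility and sample size re-assessment analysis will be evaluated for the primary endpoint", which is VH 0 response at Month 5. The analysis set, however, is defined by Month 3: randomized subjects who "received at least one dose of IP at baseline, and reached or completed Month 3 visit of the study". For outcomes not yet available, the same section states: "Missing VH status at the interim analysis will be handled using the multiple imputation approach in the similar manner as specified in Section 8.2.1". In SAP 8.2.1 the CMH statistic from each of 50 completed datasets "will be transformed using Wilson-Hilferty transformation and combined for inference purposes".

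The conditional-power formula in SAP 5.5.1 takes two interim inputs. The first, n1, "is the number of evaluable subjects at the interim analysis". For the second, "z_1 is the squared root of the CMH test statistic as computed at the interim analysis of n_1 evaluable subjects". The word 'evaluable' is not defined. The section defines the estimated rate difference (440 µg minus sham) but never uses it to sign z1.

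The decision rules are futility below 30%, an increase of up to 100 subjects between 50% and 80%, and no change otherwise.

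**The concern.** Month 3 is Day 90 and Month 5 is Day 150. While enrolment is open, the Month 3 condition therefore brings in subjects whose Month 5 visit is up to about 60 days away. Unless they are already non-responders under SAP 8.2.1, their Month 5 status at the interim is imputed.

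The formula uses n1/n2 as the information fraction, and z1 is computed on the same n1 subjects. Imputed outcomes are therefore weighted as if they had been observed. For a given z1, a larger n1 gives a smaller conditional power in the range where decisions are made. A viable trial could be recommended for futility, or miss a sample-size increase at the 50% limit.

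The sign is a second defect in the same formula. The square root of a CMH chi-square statistic is never negative, so the formula as printed cannot distinguish an interim favouring DE-109 from one favouring sham. Both interim decisions depend on this single number.

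**Working it through.** **Design figure.** Inputs from SAP 3.3: 30% vs 12%, two-sided α = 0.05, 80 per arm. The Pearson chi-square sample size reproduces as 80 per arm, with power 80.4%. The expected final z is therefore 1.960 + 0.856 = 2.816.

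**Formula.** With t = n1/n2, the expression in SAP 5.5.1 simplifies to

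CP = Φ[(z1/√t − 1.960)/√(1 − t)].

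Only z1 and t enter.

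**Baseline.** Under 2:2:1 allocation, 100 subjects completing Month 5 give about 80 in the two compared arms, so t = 80/160 = 0.50. (Counting all arms gives 100/200, the same ratio.) CP of 30/50/80% then corresponds to z1 = 1.124/1.386/1.807.

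**Assumed inputs.** The documents give no accrual rate. I take 5, 10 or 20 subjects per month over the two months between visits. That is 10, 20 or 40 subjects over all arms, hence 8, 16 or 32 in the compared arms, and n1 = 88, 96 or 112. The documents also do not say how well earlier haze predicts Month 5. Finally, I assume that the combined z1 reflects the imputation uncertainty.

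**Upper bound: imputed subjects add no information (true t = 0.50).**

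| n1 used | t used | True CP 30/50/80% is computed as | True CP at the nominal 30% line |
|---|---|---|---|
| 88 | 0.55 | 25/45/76% | 35% |
| 96 | 0.60 | 21/39/72% | 40% |
| 112 | 0.70 | 13/29/64% | 51% |

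Example at n1 = 96, true CP 50%: (1.386/√0.60 − 1.960)/√0.40 = (1.789 − 1.960)/0.632 = −0.27, and Φ(−0.27) = 39%.

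**Partial recovery.** If earlier haze recovers half of each of the 16 imputed outcomes, the effective n is 80 + 8 = 88 (true t = 0.55). True CP of 30/50/80% is then computed as 25/45/77% at n1 = 96.

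**Simulation check.** The model was a normally distributed latent haze score with correctly specified regression imputation by arm, a Month 3 to Month 5 correlation of 0 to 0.7, and 1,500 replicates. The effective n was about 90 to 95 for a nominal 96, and about 95 to 106 for a nominal 112. In that favourable model the overstatement is smaller than the upper bound, but it is still present.

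**Chance of a futility signal under 30% vs 12%.** P(CP < 30%) = Φ(z_cut − 2.816·√t_true). With n1 = 80 this is Φ(1.124 − 1.991) = 19.3%. With no information added, the cut-offs of 1.193, 1.261 and 1.400 for n1 = 88, 96 and 112 give 21.2%, 23.3% and 27.7%. With half recovery at n1 = 96, the chance moves from 18.5% to 20.4%.

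**Sign of z1.** Suppose the interim favours sham with |z1| = 1.5 at n1 = 80. As printed, (1.5/√0.50 − 1.960)/√0.50 = (2.121 − 1.960)/0.707 = 0.23, so CP = 59%, in the promising zone. With the sign, (−2.121 − 1.960)/0.707 = −5.77, so CP is about 0%, which is futility.

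**The case against.** - **'Evaluable' may mean known Month 5 status.** In that case n1 is right. The term is undefined and Protocol 9.6 defers detail to a DMC charter that is not available here, so this cannot be excluded. It fits the text poorly, because z1 comes from the same n1 subjects and the analysis set is defined by Month 3. If it is the intent, it needs to be written.
- **The effect may be small.** This stands in part. Imputation draws on earlier visits, so these subjects contribute some information, and the no-information figures are a bound. The futility signal rises by about 2 to 8 percentage points at that bound, and by about 2 with half recovery at n1 = 96. Futility is advisory, and there is no early efficacy stop.
- **Direction is visible anyway.** The section defines the signed rate difference, so a competent analyst would probably notice a reversed effect. A pre-specified rule should not depend on that.

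A reader might also infer more than the documents support:

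- **That all Month 5 outcomes at the interim are imputed.** About 80 compared-arm subjects will have completed Month 5, and rule-based non-responders need no imputation.
- **That later Month 5 results from subjects in the pipeline destroy the independence of the two stages.** With the correct information fraction the increments are approximately independent. This is the same information-fraction error, not a second one.
- **That the 50% limit becomes anti-conservative.** Overstating n1 biases conditional power downward, so the zone is entered at a true value above 50%.

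**Conclusion.** The conditional-power calculation is wrong as written in two respects.

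First, the Month 3 analysis set and the Month 5 endpoint are not reconciled, and nothing adjusts n1/n2 for imputed outcomes. This makes conditional power too low. The direction follows from the printed formula, the natural reading of 'evaluable', and a combined z1 that carries the imputation uncertainty. The size depends on accrual and on the information recovered by imputation, neither of which the documents give. The plausible effect runs from slight to a computed 13/29/64% in place of 30/50/80% (n1 = 112, no information recovered).

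Second, the loss of sign in z1 needs no assumption about accrual. A sham-favouring interim can be placed in the promising zone.

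This should be corrected because both interim decisions use this number. It is not evidence of inflated type I error.

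**What to change.** Define 'evaluable' in SAP 5.5.1 and compute z1 and n1 on the same set, by one of two routes:

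1. Use subjects in the two compared arms whose Month 5 visit window has closed. Include those who left or were rescued earlier and are non-responders under SAP 8.2.1; the present Month 3 condition may drop some of them. Apply imputation only within this set.
2. Keep the Month 3 set, and replace n1/n2 with an information fraction obtained from the variance of the combined estimate. This retains the partial data.

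Under either route, give z1 the sign of the estimated rate difference (440 µg minus sham), and state that n1 and n2 exclude the dummy arm.

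The cost is wording in the SAP and the DMC charter, plus slightly fewer subjects at the interim under the first route.
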